**Protocol Summary**

Title	Off label study to evaluate the efficacy of hydroxychloroquine as prophylaxis to prevent severe acute respiratory syndrome coronavirus 2 (SARS-CoV-2) infection among Health Care Workers (HCWs) who are at high risk of occupational exposure to SARS-CoV-2 Short Study Title: COVID-19 HCWP HCQ Study
Brief Summary	The HCW Prophylaxis (HCWP) Study, single, open and off label intervention study. Up to 350 participants will be assigned to group that takes HCQ or group that opts to not take study medication. Participants will be UNM HEALTH SYSTEM HCW at high risk for occupational exposure to SARS-CoV-2. Study timepoints will include Day 1 screening/enrollment, 30 day, 60 day, and 90 day assessments. Questionnaires will be collected in all timepoints.
Phase	Off label use of HCQ
Primary Objectives	To evaluate the efficacy of hydroxychloroquine (HCQ) for prophylaxis (HCWP) to prevent severe acute respiratory syndrome coronavirus 2 (SARS-CoV-2) infection among Health Care Workers High Risk of Occupational Exposure to SARS-CoV-2
Methodology	The Health Care Worker Prophylaxis (HCWP) Study, single, open and off label intervention study
Primary Endpoint	Number of HCW who test positive for SARS-CoV-2 while in the trial as determined by polymerase chain reaction assays from standard of care swaps.
Study Duration	12 months
Participant Duration	Participant Study period: up to 90 days for both groups, inclusive of those who elect to convert from Group B to Group A.
Duration of IP administration	Up to 90 days
Population	Total number of participants: Up to 350 UNM HEALTH SYSTEM health care workers with high risk of occupational exposure to SARS-CoV-2 Group A: up to 275 (HCW choose to be provided HCQ) Group B: up to 75 (HCW choose not to be provided HCQ)
Study Sites	UNM HEALTH SYSTEMS
Number of participants	Up to 350
Description of Study Agent/Procedure	Hydroxychloroquine- oral administration 
 
• Duration: up to 90 days or until meeting study termination criteria
 
• Loading dose: 600 mg once for the first day
 
• Maintenance dose: 200 mg, daily
 
 
Hydroxychloroquine is licensed for the chemoprophylaxis and treatment of malaria and as a disease modifying antirheumatic drug. It has a long history of being safe and well tolerated at typical doses. HCQ has antiviral activity in vitro against coronaviruses, and specifically Covid-19.

Key Procedures	Questionnaires

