### **2.2 Risks**

#### **2.2.1 Risk of study agent**

To account for possibilities of drug interactions, we have excluded a small list of anti-arrhythmic because of a theoretic concern of the effects on prolonged QTc interval. Additional drug interactions listed in the monograph are not expected to be clinically relevant at the doses and duration being prescribed. The PI's will monitor subjects who develop side effects. The only anticipated side effect we expect to see in 1-2% of the subject population is mild, self-limited drug reaction presenting as skin rash. More rarely, the drug has been associated with Stevens-Johnson Syndrome and Toxic Epidermal Necrolysis, therefore subjects who experience rash will be asked to discontinue HCQ. Additionally, dyspepsia may be encountered with drug administration – not ulcerogenic. This tends to be mild and self-limiting. The drug can be taken with food. Recommendation to subjects is to avoid antacids and cimetidine, as they reduce bioavailability. Alternatives include proton pump

inhibitors and other histamine 2 blockers. As with any experimental treatment for specific diseases, there may be unknown or unforeseeable side effects.

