## 4.6 Participant Withdrawal or Termination

Reasons for early Withdrawal or Termination

- Participants become PCR-confirmed SARS-CoV-2 status
- Participant starts disallowed medication (Group A only)
- Advent of an adverse event which necessitates discontinuation of HCQ (Group A only, see section 6)
- Participant decides to withdraw from the study
- PI discontinues participation due to safety concerns
- Participant decides to withdraw consent
- Participant's primary care provider determines the study is not in participant's best interest
- PI decides to withdraw participant due to non-compliance

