### 5.2 Study Schedule

#### 5.2.1 Schematic of Study Design

##### Schematic of Study Design

**Schedules of Activities for COVID-19 HCWP HCW HCQ Study**

Task	Screening/ Baseline	Daily (existing required survey)	30 Day (± 7days)	60 Day (± 7days)	90 Day (± 7days)	Early Termination or Clinically Suspected SARS- CoV-2
Consent	X					
Health history	X					
Exposure Survey (online)	X	X				X
Swab* for SARS-CoV-2 and plasma/serum sample	X		X	X	X	X
Hydroxychloroquine dosing initiation	X					
Adverse Events		X	X	X	X	X

\*Lab has confirmed ability to test samples from week over next weekend. Estimate up to 50 total per week (25 Sat, 25 Sun). Lab has also agreed to bank plasma and serum samples for delayed analysis.

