### **5.2.4 Early Termination Visit**

Early termination visit will consist of questionnaire and nasal swab.

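### Two exit reasons that apply to Group A only shorten infection follow-up in that group alone, and the plan has no rule for classifying early leavers in the yes/no primary endpoint

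*Combined protocol and SAP*

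**What the plan says.** Section 4.6 gives eight reasons for early withdrawal or termination in one list. Two are restricted to Group A: "Participant starts disallowed medication (Group A only" and "Advent of an adverse event which necessitates discontinuation of HCQ (Group A only, see section 6". The other six are not restricted by group. The list does not separate stopping the drug from leaving the study, and the Protocol Summary ties the duration of HCQ to the study termination criteria.

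Section 2.2.1 gives the only rate for an event that leads to stopping: "The only anticipated side effect we expect to see in 1-2% of the subject population" is a skin rash, and "therefore subjects who experience rash will be asked to discontinue HCQ". It adds that "dyspepsia may be encountered with drug administration", without a rate. No rate is given for starting a disallowed medication.

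SARS-CoV-2 testing is planned at enrollment and days 30, 60 and 90 (5.1.1, 5.3). For those who leave early, 5.2.4 says: "Early termination visit will consist of questionnaire and nasal swab". After participation ends, 6.4 describes recording of adverse events for 7 days (30 for serious events), with no further PCR.

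The Protocol Summary defines the primary endpoint as "Number of HCW who test positive for SARS-CoV-2 while in the trial". Section 7.4.2 treats it as binary, and 7.3 takes the primary analysis set to be all enrolled participants. The single sensitivity analysis uses HCQ participants who finish their course. No section gives a censoring, person-time or missing-outcome rule.

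**The concern.** A yes/no endpoint without time at risk compares groups fairly only if they are watched for about the same time. Here a written rule ends observation for reasons that cannot arise in Group B. An infection after the exit swab goes unseen in such a Group A participant, while a Group B participant is swabbed to day 90.

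Section 7 does not say what becomes of a leaver whose exit swab was negative. The analyst would have to decide after seeing data, in an open-label comparison of self-selected groups. Matching and logistic regression (7.4.2) are aimed at exposure risk, demographics and comorbidities, not follow-up time. The completers analysis removes the same people from Group A alone.

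**Working it through.** **The plan's own figure.** The documents give no figure for early exit. The nearest is in 7.5: 80% power for 35% v 20% when two-thirds take HCQ (table row 230/120). The pooled two-proportion formula gives 85.7%, or 82.7% with continuity correction. The stated figure is therefore somewhat conservative, and nothing below rests on it.

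**Inputs from the documents.** Group sizes 275 and 75 (4.2.1); 90 days (4.4); two-sided 0.05 (7.4.1); 35% risk, an illustrative control rate (7.5); rash 1-2% (2.2.1).

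**Assumptions.** No HCQ effect; constant hazard; stops at day 15 to 45; no Group B exits; leavers with a negative exit swab counted as not positive. Also assumed: a 10% risk as a lower alternative, and a 10% stopping rate to show how the effect grows.

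**Formulas.** With 90-day risk p, hazard h = -ln(1-p)/90. Risk by day t is q = 1 - exp(-h*t). If a share d of Group A stops at day t, its observed rate is (1-d)*p + d*q, so the shift is d*(p - q). Rejection is that of the pooled z-test, which is nearly identical to a tie-corrected Wilcoxon rank-sum test on 0/1 data.

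**Numbers at p = 0.35.** h = -ln(0.65)/90 = 0.004786, so q = 0.0693 at day 15 and 0.1938 at day 45.

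- d = 0.02: 0.02 x (0.35 - 0.0693) = 0.0056; 0.02 x (0.35 - 0.1938) = 0.0031.
- d = 0.01: 0.0028 and 0.0016.
- d = 0.10: 0.0281 and 0.0156.

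| Risk | Share of Group A stopping | Shift, points | Expected positives missed of 275 | Two-sided rejection |
|---|---|---|---|---|
| 35% | 1-2% (documented, rash only) | 0.2-0.6 | 0.4-1.5 | 5.0-5.1% |
| 35% | 10% (assumed) | 1.6-2.8 | 4.3-7.7 | 5.9-7.7% |
| 10% | 1-2% | 0.05-0.17 | 0.1-0.5 | 5.0-5.1% |
| 10% | 10% (assumed) | 0.5-0.8 | 1.3-2.3 | 5.5-6.1% |

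**If leavers are dropped instead**, and leaving is unrelated to infection, the shift is 0. Power for 35% v 20% at 275/75 falls from 75.9% to 75.7% (2% stop, 270 left) or 74.8% (10% stop, 248 left).

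**Offset from Group B.** The same formula applies to Group B exits. One exit is 1/75 = 1.3% and two are 2.7%. At day 15 and 35% risk they shift Group B by 0.0133 x 0.2807 = 0.37 points and 0.0267 x 0.2807 = 0.75 points, against 0.28 and 0.56 points for 1% and 2% of Group A. Equal exit shares and times in both groups give a shift of 0.

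**The case against.** The strongest reply is that the effect is negligible on the plan's own evidence. At 1-2% stopping, type I error barely moves, and the larger figures need an assumed rate. That stands as to size. It does not bound the problem, because the 1-2% covers rash only and total Group A-only stopping is not given.

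Second, 4.6 may simply mix drug-stopping with study-leaving reasons: 2.2.1 asks people with rash to discontinue HCQ and does not say that they leave. That reading is possible, but 4.6 literally lists these events as reasons for withdrawal or termination, so the text needs reconciling on either reading.

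Third, direction. A reader might infer that the plan builds in a bias favouring HCQ. The documents do not support that. The coding of leavers is unstated, and six of the eight exit reasons are open to both groups. One of the six is PCR positivity, which is the endpoint itself; the other five can end follow-up without an event in either group. One or two extra exits among 75 could reverse the sign. Switching from Group B to Group A (5.2.3) can also shorten untreated time in Group B.

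A reader might also infer that leavers have no infection assessment. That is wrong: a swab is taken at exit, and the gap begins after it.

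Last, censoring does not fit the binary Wilcoxon and logistic analysis in 7.4.2. That is correct, so follow-up time belongs in a named additional analysis.

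**Conclusion.** The point holds as a gap in the rules for follow-up and classification, worth fixing because the fix is cheap. Section 4.6 as written shortens observation in one group only for two reasons, and section 7 neither accounts for this nor says how leavers are counted.

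A tilt toward HCQ follows only if leavers with a negative exit swab are counted as not positive and other exits are balanced. On those conditions it is at most about 0.6 points at the documented rash rate and 35% risk. It reaches 1.6-2.8 points only at an assumed 10% stopping rate. The documents do not establish material bias or a certain net direction. Confidence is medium, since the total stopping rate and the coding are both unstated.

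**What to change.** Leave the criteria for stopping HCQ, and the other six exit reasons, unchanged.

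1. In 4.6, state that the two Group A-only reasons concern study drug and do not by themselves end follow-up. With consent, keep those participants on the day 30, 60 and 90 swabs and surveys already scheduled, and analyse them in Group A.
2. In section 7, state how true leavers in either group are handled, and do not count them as negative in the primary analysis by default. Report exits by group and reason.
3. Add a sensitivity analysis that accounts for follow-up time, such as interval-censored or discrete-time regression over the 30-day swab intervals. State its assumption that leaving is unrelated to infection risk given the covariates.

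Cost: a protocol amendment, one added analysis and a few extra contacts. At the documented rate this concerns about 3-6 people (275 x 0.01 = 2.75; 275 x 0.02 = 5.5), each with at most three remaining swabs, so at most 18. These must fit the laboratory estimate of up to 50 tests a week (5.2.1) and the swab supply that 5.3 leaves to a later modification.

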### 3 Objectives

Primary Objective	Primary Endpoint
To evaluate the efficacy of hydroxychloroquine (HCQ) for prophylaxis to prevent severe acute respiratory syndrome coronavirus 2 (SARS-CoV-2) infection among HCWs at high risk of occupational exposure to SARS-CoV-2 compared to eligible cohort that declines treatment	Frequency of infection with SARS-CoV-2 as determined by positive PCR for the virus on standard diagnostic tests.
Secondary Objectives	Secondary Endpoints
1. To characterize whether high-risk HCW who test positive for SARS-CoV-2 have an asymptomatic infection or report symptoms of COVID-19 in the 4 weeks preceding positive SARS-CoV-2	1. Symptom questionnaires performed once daily as currently mandated for HCW in high risk settings within UNMHS.
2. Determine role of occupational health exposure risk level on subsequent conversion frequency (mild-moderate-severe)	2. Online survey required once daily for all at risk HCW (existing document)
3. To assess the severity of any SARS-CoV-2 infection after prophylactic treatment with hydroxychloroquine.	3. Symptom questionnaires, Hospital admission rate, ICU admission rate, Mortality rate, PSI score of respiratory compromise
4. To assess the tolerability of hydroxychloroquine prophylaxis of SARS-CoV-2 in this population	4. Incidence of AEs or SAEs related to HCQ at study termination.
Exploratory Objectives	Exploratory Endpoints
1. To determine whether hydroxychloroquine reduces time lost from work	1. Days away from work
2. To assess the compliance of hydroxychloroquine prophylaxis	2. Frequency of missing dose
3. To assess whether HCQ benefits are different for specific AGPs or exposure on certain covid units (MICU v. ED v. covid rule out unit)	3. Frequency of positive test for SARS-CoV-2 related to AGP's or specific Covid-19 units.
4. To compare seroconversion between HCQ-treated and HCQ-untreated subjects on blood or plasma specimens.	4. Serological analyses at 4 times points (baseline, 30,60 and 90 days of study enrollment---with a 7-day window after each time point to complete analyses)

5. Metagenomic next generation sequencing of SARS-CoV-2 isolates detected in subjects	5. Sequence of viral isolates compared to published genomes and community-circulating SARS-CoV-2
---	--

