#### 4.2.1.1 Inclusion Criteria

1. Men or women  $\geq 18$  years of age who are UNM HEALTH SYSTEM health care workers and are asymptomatic for known presenting symptoms of SARS-CoV-2:
2. UNMHS HCWs include: MD/DO, NP, RN, and respiratory therapists working in ED, Pediatric ED, Urgent Care, Pediatric Urgent Care or on Covid-19 units. Study PI's will consider study enrollment of HCWs from other settings, for example certain outpatient clinics or inpatient units.
3. Are not positive for SARS-CoV-2 testing
4. Willing and able to comply with survey completion, scheduled visits, treatment plan, and other study procedures
5. Willing and able to provide informed consent

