## 5 Study Procedures and Schedule

### 5.1 Study Procedures/Evaluations

#### 5.1.1 Study Specific Procedures

##### Employee Exposure Survey and Aerosol Generating Procedures (Appendix A)

Participants from both Group A and B will be asked to complete the Employee Exposure Survey. This online instrument asks health care providers currently working in at risk units to report symptoms or exposures (eg. AGPs) related to their encounters with patients who have or are suspected of Covid-19. These HCWs are reminded to complete the Survey once per day. The link to this REDCap survey is currently being emailed to UNMHSC HCWs and they can access it through widely distributed QR codes. Given its active use, this survey will not add additional stress or workload to study participants. Additional study specific questions will be added to this survey and the data is linked to REDcap a database.

Confirmation of Pregnancy in Women of Childbearing Potential: We will document in subject's research record whether they are pregnant based on self-report and date of last menses (at Screening and follow-up visits). Pregnancy is not a contraindication for receiving HCQ.

A list of potential Aerosol Generating Procedures (AGP) is also provided in Appendix A.

Subjects will only be asked to complete SARS-CoV-2 testing at study enrollment and the 30, 60 and 90 day follow up points, with a 7-day window after each time point to complete the testing.

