#### 5.2.2 Screening and Enrollment Visit

Both Screening and Enrollment visits can occur on the same day. Participants will be assessed for study eligibility through a pre-screening visit which may be conducted via telephone and include completion of the Employee Exposure Survey. Those who decide to take HCQ will be the experimental group (Group A), and participants who choose not to take HCQ will be part of the control group (Group B).

The Employee Exposure Survey can be accessed online via the following URL: <https://is.gd/reportexposure>. It can also be accessed by this QR code placed strategically in relevant patient care areas:

A hard copy of the survey is also attached as an appendix at the end of this protocol document. Questions relevant to this study will be added to the survey if the respondent indicates they are a study participant. We will use the REDcap database to track adherence to the protocol required surveys and send email or phone reminders if more than 2 days are missed.

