### **10.2 Protocol Deviations**

A protocol deviation is any noncompliance with the clinical trial protocol, GCP, or Manual of Procedures (MOP) requirements. The noncompliance may be either on the part of the participant, the investigator, or the study site staff. As a result of deviations, corrective actions are to be developed by the site and implemented promptly.

Protocol deviations must be reported to the local IRB per their guidelines. The site PI/study staff is responsible for knowing and adhering to their IRB requirements. Further details about the handling of protocol deviations will be included in the MOP.

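### Section 4.6 lets the PI end participation for undefined non-compliance, which can cut short the missed-dose data for exploratory endpoint 2 and forfeit later scheduled swabs

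*Combined protocol and SAP*

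**What the plan says.** Section 4.6 of the combined protocol and SAP gives the reasons for early withdrawal or termination. One is "PI decides to withdraw participant due to non-compliance". It has no definition and no threshold. Other items in the list are limited to the treated group, for example "Participant starts disallowed medication (Group A only"), but this one is not.

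Section 3 sets exploratory objective 2, "To assess the compliance of hydroxychloroquine prophylaxis", with the endpoint "Frequency of missing dose". Section 7 adds no denominator, analysis set or handling of withdrawals for it. Section 7.3 defines the primary analysis set as all enrolled participants, and keeps the subset completing HCQ for sensitivity analyses.

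Sections 5.1.1 and 5.3 schedule swabs at baseline and days 30, 60 and 90. Section 5.2.4 adds a questionnaire and swab at early termination. Section 10.2 treats participant noncompliance as a protocol deviation: "As a result of deviations, corrective actions are to be developed by the site and implemented promptly".

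**The concern.** A rule that ends follow-up because of poor compliance, in a study that also measures compliance, can select on the outcome. The study is open label, so the PI can know who is taking HCQ, and the decision is left to judgement. Once a poor adherer leaves, later missed doses go unobserved, and that person contributes fewer days to any summary that weights by time on study.

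Two things are at stake. The first is a fair answer to exploratory objective 2, which also helps to interpret a null efficacy result: whether the drug did not work or was not taken. The second is outcome data. The Protocol Summary counts positives found while a participant is in the trial, so someone withdrawn for non-compliance stays in the all-enrolled primary set but is no longer tested on the remaining scheduled occasions.

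**Working it through.** The documents give no figure for adherence, missed doses or withdrawal for non-compliance, so there is no stated result to reproduce. What follows is an illustration on assumed inputs.

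**Inputs.** From the documents: about 90 planned dosing days (Section 4.7.1.2) and Group A of up to 275 (Section 4.2.1). Assumed: a share s of Group A is withdrawn at day 30, having missed a fraction m = 0.5 of doses by then; everyone else misses 5%.

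**Formulas for the missed-dose frequency.**
- Pooled on-study days: [(1−s)·90·0.05 + s·30·m] / [(1−s)·90 + s·30]
- Completers only: 0.05
- Mean of each participant's own on-study proportion: (1−s)·0.05 + s·m
- Reference 1, everyone followed and the same pattern continues: [(1−s)·90·0.05 + s·90·m] / 90
- Reference 2, everyone followed and the poor adherers take nothing after day 30: [(1−s)·90·0.05 + s·(30·m + 60)] / 90

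**Results.**

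| Summary | s = 0.10 | s = 0.20 |
|---|---|---|
| Pooled on-study days | 5.55/84 = 6.6% | 6.60/78 = 8.5% |
| Completers only | 5.0% | 5.0% |
| Mean of per-participant proportions | 0.045 + 0.050 = 9.5% | 0.040 + 0.100 = 14.0% |
| Reference 1 | 8.55/90 = 9.5% | 12.60/90 = 14.0% |
| Reference 2 | 11.55/90 = 12.8% | 18.60/90 = 20.7% |

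Against reference 1, pooling understates missed dosing by 9.5 − 6.6 = 2.9 points at s = 0.10 and by 14.0 − 8.5 = 5.5 points at s = 0.20. The mean of per-participant proportions has no bias. Against reference 2, where the miss rate worsens, that mean is also too low, by 12.8 − 9.5 = 3.3 and 20.7 − 14.0 = 6.7 points. The zero therefore depends on a constant miss rate.

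**Wider range.** With s from 5% to 20%, m from 40% to 60% and withdrawal at day 30 or 60, measured against reference 1, compliance is too high by 0.6 to 6.8 points with pooled days and by 1.8 to 11.0 points if withdrawn people are dropped. The per-participant mean has no bias. If all planned days after withdrawal are counted as missed, compliance is too low by 0.7 to 8.0 points.

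**Swabs.** Someone withdrawn at day 30 forfeits the day 60 and day 90 swabs, two of the three scheduled after baseline. In a Group A of 275, s = 0.10 means 27.5 × 2 = 55 of 275 × 3 = 825 scheduled swabs (6.7%), and s = 0.20 means 110 of 825 (13.3%). The early termination swab replaces part of this.

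**The case against.** The strongest reply is that the documents show no certain bias. Section 4.6 ends participation; it does not discard data. The early termination questionnaire is still collected, and Section 9.4 keeps data gathered before authorization is revoked, which is a stricter case. Missed doses up to withdrawal can still be counted, and a mean of per-participant proportions is as natural a summary as pooled days. All this stands. A reader might infer that reported compliance must come out too high, or that poor adherers vanish from the data. Neither follows from the text.

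Nor does the text say that non-compliance means missed HCQ doses. Participants agree at entry to be "Willing and able to comply with survey completion, scheduled visits, treatment plan, and other study procedures", and the item also covers Group B, who take no HCQ. The only adherence tracking described is of surveys: the plan will "track adherence to the protocol required surveys and send email or phone reminders if more than 2 days are missed". Selection on missed doses is thus possible under the rule, but it is not documented. The reply does not remove the concern, because the treatment plan is among the things to be complied with. Section 5.1.1 also says "Additional study specific questions will be added to this survey". If those questions cover dosing, withdrawal for missed surveys cuts the adherence record short as well.

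A reader might also take Section 10.2 to make withdrawal redundant or to contradict Section 4.6. It does neither: it does not list the corrective actions, and it leaves further detail to a manual of procedures that is not part of these documents. That manual or the survey, which is attached but not shown, may hold a threshold or a dose question.

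Finally, counting every planned day after stopping as missed would be a poor remedy. Section 4.6 itself directs some stops. Taking the 20% HCQ-group positivity from the Section 7.5 example and assuming an average stop at day 45, this adds 0.20 × 45/90 = 10 points of apparent missed dosing, more than the 2.9-point bias above.

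**Conclusion.** The concern holds in a limited form. The plan states a rule that can end follow-up selectively in poor compliers, and it leaves the endpoint most affected without a denominator. Missed dosing is likely to be understated if it is summarised over pooled on-study days or in completers: 6.6% against 9.5% with an assumed 10% withdrawn, and 8.5% against 14.0% with 20%. It need not be understated under per-participant proportions with a constant miss rate. These sizes rest on assumed withdrawal shares and miss rates.

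The loss of later swabs follows directly from the rule and sits badly with an all-enrolled primary set. Its extent is unknown because no withdrawal rate is given. A reader might infer that the primary comparison is biased in a particular direction. The documents do not support that, since the rule covers both groups and nothing shows how often it would be used in each.

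The point is minor: the objective is exploratory, has no stated test, and withdrawal is discretionary.

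**What to change.** Remove non-compliance from the Section 4.6 reasons for ending study participation and handle it as a deviation under Section 10.2. Keep these participants in the surveys and the scheduled day 30, 60 and 90 assessments unless they withdraw consent. The other reasons in Section 4.6 are not affected.

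Define the missed-dose endpoint for all Group A participants as missed doses over the days on which dosing was still planned, and state how missed doses are recorded. Report discontinuation of HCQ and its reason separately, so that stops directed by Section 4.6 (PCR positivity, adverse event, disallowed medication) are not counted as missed doses. Say in advance how a participant's own decision to stop is classified, and whether the summary pools days or averages participants. With equal follow-up both give 9.5% or 14.0% on the inputs above, so the choice matters much less.

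Whether HCQ itself continues is a clinical matter and is not addressed here. The cost is protocol wording, since the surveys and assessments are already scheduled and Section 4.5 makes visits after enrollment remote. The small downside is reminder effort for people who respond poorly.
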